4.4. End of Study Definition

The end of the study is defined as the date of the last visit of the last participant in the study.

A participant is considered to have completed the study if the participant has completed all periods of the study including the last visit.

5. Study Population

Eligibility of participants for enrollment in the study will be based on the results of screening medical history, physical examination, vital signs, clinical laboratory tests, and ECG. The nature of any conditions present at the time of the physical examination and any preexisting conditions will be documented.

The inclusion and exclusion criteria used to determine eligibility should be applied at screening only unless otherwise specified, and not continuously throughout the trial.

Screening may occur up to 28 days prior to enrollment. Participants who are not enrolled within 28 days of screening may undergo an additional medical assessment and/or clinical measurements to confirm their eligibility.

Prospective approval of protocol deviations to recruitment and enrollment criteria, also known as protocol waivers or exemptions, is not permitted.

5.1. Inclusion Criteria

Participants are eligible to be included in the study only if all of the following criteria apply:

Age

1. Participant must be 18 to 40 years of age inclusive, at the time of signing the informed consent.

Type of Participant and Disease Characteristics

2. Participants who are overtly healthy as determined by medical evaluation including medical history, physical examination, laboratory tests, vital signs, and cardiac monitoring

Weight

3. Body mass index (BMI) within the range of 19.0 to 32.0 kg/m² (inclusive).

Sex and Contraceptive/Barrier Requirements

4. Male or female

Women of childbearing potential will be excluded from the study.

Contraceptive use by participants should be consistent with local regulations regarding the methods of contraception for those participating in clinical studies. For the contraception requirements of this protocol, see Appendix 10.4.

Informed Consent

5. Capable of giving signed informed consent as described in Appendix 1 (Section 10.1), which includes compliance with the requirements and restrictions listed in the informed consent form (ICF) and in this protocol.

Other Inclusions

6. Clinical laboratory test results within normal reference range for the population or investigator site, or results with acceptable deviations that are judged to be not clinically significant by the investigator.
7. Venous access sufficient to allow IV drug delivery and blood sampling as per the protocol.
8. Are reliable and willing to make themselves available for the duration of the study and are willing to follow study procedures and research unit policies.

5.2. Exclusion Criteria

Participants are excluded from the study if any of the following criteria apply:

Medical Conditions

9. Have a history of intracranial hemorrhage, cerebrovascular aneurysm or arteriovenous malformation, carotid, carotid artery occlusion, stroke or epilepsy or family history of dementia or Down's syndrome.
10. Have a history or presence of cardiovascular, respiratory, hepatic, renal, gastrointestinal, endocrine, hematological, immunological, or neurological disorders capable of significantly altering the absorption, metabolism, or elimination of drugs; or constituting a risk when taking the study medication; or of interfering with the interpretation of data.
11. Have allergies to either humanized monoclonal antibodies, diphenhydramine, epinephrine, or methylprednisolone.
12. Have had gamma globulin therapy within the last 6 months.
13. Have a history within the past 5 years of a primary or recurrent malignant disease.
14. Have a history of clinically significant multiple or severe drug allergies or severe posttreatment hypersensitivity reactions (including but not limited to erythema multiforme major, linear immunoglobulin A dermatosis, toxic epidermal necrolysis, exfoliative dermatitis).
15. Are, in the judgment of the investigator, actively suicidal and therefore deemed to be at significant risk for suicide.
16. Have answered "yes" to either Question 4 or Question 5 on the "Suicidal Ideation" portion of the Columbia-Suicide Severity Rating Scale (C-SSRS) or have answered "yes" to any of the suicide-related behaviors on the "suicidal behavior" portion of the C-SSRS, and the ideation or behavior occurred within the past month.
17. Have a history or presence of psychiatric disorders considered to be clinically significant in the opinion of the investigator.
18. Have evidence of human immunodeficiency virus (HIV) infection and/or positive HIV antibodies.
19. Have spontaneously cleared hepatitis C virus (HCV) infection, defined as a positive HCV antibody test and a negative HCV RNA test. Participants with no history of HCV antibody (anti-HCV) treatment, may be eligible for inclusion in the study, provided they have no detectable HCV RNA at screening for this study.

20. Have a current infection with hepatitis B virus (HBV), that is, positive for hepatitis B surface antigen, polymerase chain reaction (PCR) positive for HBV DNA or both.
21. Are lactating.

Prior/Concomitant Therapy

22. Have used over-the-counter or prescription medications, including herbal medication, within 7 days prior to dosing.

Prior/Concurrent Clinical Study Experience

23. Are currently enrolled in, have completed or discontinued dosing within the last 30 days or 5 half-lives of investigational product from a clinical trial involving an investigational product; or are concurrently enrolled in any other type of medical research.
24. Have previously completed or withdrawn from this study or any other study investigating donanemab.

Diagnostic Assessments

25. Have screening clinical laboratory test results with unacceptable deviations that are judged to be clinically significant by the investigator.
26. Have an abnormality in the 12-lead ECG, abnormal blood pressure, and pulse rate considered clinically significant by the investigator.

Other Exclusions

27. Are investigator site personnel directly affiliated with the study, or are immediate family of investigator site personnel directly affiliated with the study. Immediate family is defined as a spouse, parent, child, or sibling, whether biological or legally adopted.
28. Are Lilly employees or employees of third-party organizations involved with the study.
29. Known history of alcohol or drug abuse (as defined by the Diagnostic and Statistical Manual, fifth Edition, Text Revision) within 2 years prior to enrolling or a positive result regarding use of illicit drugs on the drug screening test.
30. Have an average weekly alcohol intake that exceeds 21 units for males and 14 units for females per week, or are unwilling to stop alcohol consumption [from 24 hours prior to dosing until leaving the CRU] (1 unit = 12 oz or 360 mL of beer; 5 oz or 150 mL of wine; 1.5 oz or 45 mL of distilled spirits).
31. Have donated blood of more than 400 mL within the last 3 months, or any blood donation (including apheresis) within the last 1 month, or total volume of blood donation within 12 months is 1200 mL at screening.
32. In the opinion of the investigator or sponsor, are unsuitable for inclusion in the study.
33. Are pregnant or intend to become pregnant or to breastfeed during the study.
34. Smoke more than 10 cigarettes per day or are unable to abide by investigative site smoking restrictions.

5.3. Lifestyle Considerations

5.3.1. Meals and Dietary Restrictions

- Standard meals will be provided at all times while participants are resident at the CRU, as per the CRU's policy.

5.3.2. Substance Use: Caffeine, Alcohol, and Tobacco

- During each dosing session, participants will abstain from ingesting caffeine- or xanthine-containing products (eg, coffee, tea, cola drinks, and chocolate) for 24 hours before the start of dosing until after collection of the final PK and/or pharmacodynamic sample.
- During each dosing session, participants will abstain from alcohol for 24 hours before the start of dosing until leaving the CRU.
- Participants who use tobacco products will be instructed that use of nicotine-containing products (including nicotine patches) will not be permitted while they are in the clinical unit.

5.3.3. Activity

Participants will abstain from strenuous exercise for 24 hours before each blood collection for clinical laboratory tests. Participants may participate in light recreational activities during studies (eg, watching television, reading).

5.4. Screen Failures

A screen failure occurs when a participant who consents to participate in the clinical study is not subsequently enrolled in the study.

Individuals who do not meet the criteria for participation in this study (screen failure) may not be rescreened. If applicable, participants may be re-tested at the discretion of the investigator (eg, abnormal laboratory result) before being deemed a screen failure.

5.5. Criteria for Temporarily Delaying Enrollment/Randomization/Administration of Study Intervention of a Participant

Not applicable.

6. Study Intervention(s) and Concomitant Therapy

Study intervention is defined as any investigational intervention(s), marketed product(s), placebo, or medical device(s) intended to be administered to/used by a study participant according to the study protocol.

6.1. Study Intervention(s) Administered

This table lists the interventions used in this clinical study.

Intervention Name	Donanemab
Dosage Level(s)	350 mg Q2W
Route of Administration	IV infusion

Abbreviations: IV = intravenous; Q2W = every 2 weeks.

Packaging and labeling

Study interventions will be supplied by the sponsor in accordance with current Good Manufacturing Practice. Study interventions will be labeled as appropriate for country requirements.

6.1.1. Administration Details

Donanemab will be administered as slow IV infusion over at least 30 minutes. Resuscitation equipment, emergency drugs, and appropriately trained staff must be available during the infusion and for at least 4 hours after participants have completed their infusion.

6.1.1.1. Management of Infusion Reactions

There is a risk of infusion reaction with any biological agent; therefore, all participants should be monitored closely. Symptoms and signs that may occur as part of an infusion reaction include, but are not limited to:

- fever
- chills
- nausea
- headache
- bronchospasm
- hypotension
- angioedema
- throat irritation
- rash
- pruritus
- myalgia, and
- dizziness.

In the event that a significant infusion reaction occurs, the following guidance should be followed:

- The investigational product infusion should be slowed (eg, reduce infusion rate by 50% [eg, an infusion rate of 12 mL/h becomes 6 mL/h or slower]) or stopped, depending on the symptoms/signs present:
 - if slowed, the infusion should be completed at the slower rate, as tolerated
 - if determined by the investigator that the infusion should no longer continue, no further attempts to dose the participant should be made
- Supportive care should be employed in accordance with the symptoms/signs

If a participant's infusion reaction is sufficiently severe to discontinue the infusion, subsequent infusions may be administered with premedication at the discretion of the investigator following agreement with the Lilly clinical research physician (CRP) or clinical pharmacologist.

If a participant's infusion rate is reduced due to an infusion reaction, subsequent infusions may be administered at the discretion of the investigator following agreement with the Lilly CRP or clinical pharmacologist. If further infusions are administered, the infusion rate must not exceed the slowest rate used to complete the infusion on the occasion the infusion reaction occurred. Premedication may be administered at the discretion of the investigator.

If it is determined the participant should not receive further doses of investigational product, the participant should complete AE and other follow-up procedures per Section 1.3 of this protocol.

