7.1. Discontinuation of Study Intervention

When necessary, a participant may be permanently discontinued from study intervention. If so, the participant will remain in the study and follow procedures for remaining study visits, as shown in the SoA. A participant should be permanently discontinued from study intervention if

- the participant becomes pregnant during the study,
- in the opinion of the investigator, the participant should permanently discontinue the study intervention for safety reasons
- if the investigator determines that a systemic hypersensitivity reaction has occurred related to study intervention administration, the participant may be permanently discontinued from the study intervention, and the sponsor's designated medical monitor should be notified. If the investigator is uncertain about whether a systemic hypersensitivity reaction has occurred and whether discontinuation of study intervention is warranted, the investigator may consult the sponsor.

In addition, study drug may be discontinued if participants

- answered “yes” to Question 4 or Question 5 on the “Suicidal Ideation” portion of the C-SSRS, or
- answered “yes” to any of the suicide-related behaviors on the Suicidal Behavior portion of the C-SSRS.

A psychiatrist or appropriately trained professional may assist in the decision to discontinue the participant.

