8.2.8.3. Dosing Rechallenge and Premedication for Infusions

Premedication for dosing is not planned. Dosing rechallenge is contraindicated in participants that have experienced a suspected or possible anaphylactic reaction (eg, reaction involving 2 or more organ systems [eg, mucocutaneous, respiratory, cardiovascular, or gastrointestinal systems] occurring in close proximity to dosing), in a prior dose (Sampson et al. 2006). For infusion related reactions which are not suspicious for anaphylaxis, after review of the data, and at the investigator's discretion, the participant may be rechallenged. If rechallenge is planned, the

participant may be premedicated for subsequent doses at the investigator discretion and according to local practice guidelines. Prior to initiating premedication, the investigator may consult with the sponsor. Any premedication given will be documented as a concomitant therapy.

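### Protocol Sections 6.1.1.1, 7.1 and 8.2.8.3 do not give one consistent answer on further dosing after an infusion or hypersensitivity reaction

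*Protocol*

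**What the plan says.** Three protocol sections deal with what happens after a reaction.

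- **Section 6.1.1.1 (infusion reactions).** For the reaction itself, the infusion is slowed or stopped; if the investigator decides that it should not go on, "no further attempts to dose the participant should be made". The text then turns to later doses. If the reaction was severe enough to discontinue the infusion, "subsequent infusions may be administered with premedication at the discretion of the investigator following agreement with the Lilly clinical research physician" or the clinical pharmacologist. The same agreement is needed before further infusions if the rate was only reduced.
- **Section 8.2.8.3 (rechallenge and premedication).** "Dosing rechallenge is contraindicated in participants that have experienced a suspected or possible anaphylactic reaction", with the example of a reaction in two or more organ systems close to dosing. For infusion reactions that do not raise suspicion of anaphylaxis, the investigator may rechallenge at their own discretion after reviewing the data. On premedication, "Prior to initiating premedication, the investigator may consult with the sponsor".
- **Section 7.1 (discontinuation of study intervention).** The list opens "A participant should be permanently discontinued from study intervention if". The bullet for a related systemic hypersensitivity reaction then reads "the participant may be permanently discontinued from the study intervention", with the medical monitor to be notified.

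None of the three refers to another on re-dosing, and none says which prevails. Section 8 adds generally that immediate safety concerns should be discussed with the sponsor when deciding whether a participant continues.

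**The concern.** Two investigators could treat the same reaction differently and each point to a section that supports them. The first stake is safety. Infusion reactions and hypersensitivity are named risks in Protocol Section 2.3, which also says healthy participants are expected to gain no therapeutic benefit. A contraindication in one section should not be avoidable by following another.

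The second stake is the data. SAP Section 10.3.1 takes two of the three primary parameters, Cmax,ss and AUCτ,ss, from Treatment Period 6, and the Month 3 value of AUC0-4weeks from Periods 5 and 6. A participant not re-dosed after a reaction cannot contribute an on-schedule Period 6 profile. The loss might not be neutral: Protocol Section 2.2 reports that patients with hypersensitivity events more often had high-titer TE-ADA, and SAP Section 10.4.7 plots CLss, also a Period 6 parameter, by TE-ADA status.

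**Working it through.** The plan gives no figure to reproduce here, so the check is to put typical cases through each section.

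**Case A: rash and hypotension during the infusion, infusion stopped.** Both signs are on the Section 6.1.1.1 list, which also includes bronchospasm and angioedema. They involve the mucocutaneous and cardiovascular systems, so they meet the two-organ-system example in Section 8.2.8.3.

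| Section | Result for Case A |
|---|---|
| 6.1.1.1 | Later infusions possible with premedication, if the sponsor agrees |
| 8.2.8.3 | Rechallenge contraindicated |
| 7.1 (if judged a related systemic hypersensitivity reaction) | Stem: should be discontinued. Bullet: may be discontinued |

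The first two rows conflict, because Section 6.1.1.1 makes no exception for suspected anaphylaxis.

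**Case B: fever and chills, infusion stopped or slowed, anaphylaxis not suspected.**

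| Section | Result for Case B |
|---|---|
| 6.1.1.1 | Later infusions need the sponsor physician's or clinical pharmacologist's agreement |
| 8.2.8.3 | Rechallenge at the investigator's discretion; consultation before premedication optional |

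Both allow re-dosing. They differ on whether the sponsor must agree.

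**Case C: related systemic hypersensitivity, anaphylaxis not suspected.** Section 7.1 alone gives two answers, because its stem and its bullet use different verbs. It also has no link to Section 8.2.8.3 for reactions that do raise suspicion of anaphylaxis.

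**Wording on further attempts.** If the Section 6.1.1.1 bullet means only the infusion in progress, it is compatible with the later paragraph. If it means the rest of the study, the two contradict each other. Cases A, B and C come out the same on either reading, so the point does not depend on this sentence.

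**Scale (assumed rates only).** The documents give no infusion-reaction or hypersensitivity rate for 350 mg Q2W in healthy participants. With n = 40 enrolled (Protocol Section 9.5) and an assumed per-participant rate p of any reaction raising the re-dosing question, the expected number is 40p and the chance of at least one is 1 − (1 − p)^40:

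| Assumed p | Expected number | Chance of at least one |
|---|---|---|
| 2% | 0.8 | 55% |
| 5% | 2 | 87% |
| 10% | 4 | 98.5% |
| 20% | 8 | >99.9% |

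Case A reactions would be a subset. With 6 treatment periods, a reaction at dose k leaves 6 − k doses in question, at most 5. The plan allows for 40 − 25 = 15 non-completers (37.5%), so even 8 lost participants would leave 32 before other losses.

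**The case against.** The strongest reply is that the sections can be read together. Section 8.2.8.3 is the specific rule for suspected anaphylaxis, and Sections 6.1.1.1 and 7.1 are general. Permitting discontinuation for all systemic hypersensitivity does not conflict with a contraindication for a subset. A site could also obtain the agreement in Section 6.1.1.1 while exercising the discretion in Section 8.2.8.3, and the optional consultation concerns premedication rather than the decision to re-dose. Section 8 brings the sponsor in anyway. Much of this is fair, and a cautious site could satisfy every section by applying the most restrictive one. But the protocol states no such order of precedence, and a site working only from the infusion-reaction section would not see the contraindication. The mismatch within Section 7.1 remains on any reading.

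Three stronger readings are tempting, and the documents do not support them:

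- **That Section 6.1.1.1 flatly bars and then permits re-dosing.** The bar is a sub-bullet paired with the instruction to finish a slowed infusion, and separate paragraphs cover subsequent infusions. The natural reading is the infusion in progress. What is missing is a statement of scope.
- **That Section 8.2.8.3 forbids re-dosing after any reaction.** Its next sentence expressly allows rechallenge where anaphylaxis is not suspected.
- **That the Period 6 results will be biased.** No reaction rate is given, the study is descriptive with no hypothesis test (Protocol Section 9.5, SAP Section 10.3.2), and Month 1 AUC0-4weeks needs only Periods 1 and 2. Consistent wording could still leave re-dosing to judgment, so some selection might remain.

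**Conclusion.** The inconsistency is real and should be corrected. It has three parts: later infusions allowed in Section 6.1.1.1 without excluding reactions for which Section 8.2.8.3 contraindicates rechallenge; sponsor agreement required in one section and not in the other; and a stem and bullet in Section 7.1 that disagree. The unclear scope of the wording on further attempts is minor.

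The main consequence is participant safety. The effect on who contributes Period 6 data is plausible but secondary, and its size cannot be obtained from the documents. The range of 0.8 to 8 affected participants rests entirely on assumed rates and on 40 being enrolled. The conclusion about the wording needs neither assumption.

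**What to change.** Reconcile and cross-reference Protocol Sections 6.1.1.1, 7.1 and 8.2.8.3 so that each type of reaction leads to one answer. The revised text should settle four things:

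1. Whether the permission for later infusions in Section 6.1.1.1 applies to reactions covered by the Section 8.2.8.3 contraindication.
2. Whether sponsor agreement is required or optional before re-dosing, and before premedication.
3. Whether discontinuation under the Section 7.1 hypersensitivity bullet is mandatory or optional, and how it relates to Section 8.2.8.3.
4. Whether the wording on further attempts covers the infusion in progress or all later doses.

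The clinical rule is for the sponsor to choose; this review does not propose one. The cost is protocol wording, with no added visits, samples or procedures.

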6.2. Preparation, Handling, Storage, and Accountability

1. The investigator or designee must confirm appropriate storage conditions have been maintained during transit for all study intervention received and any discrepancies are reported and resolved before use of the study intervention.
2. Only participants enrolled in the study may receive study intervention. Only authorized study personnel may supply, prepare, or administer study intervention. All study intervention must be stored in a secure, environmentally controlled, and monitored (manual or automated) area in accordance with the labeled storage conditions with access limited to the investigator and authorized study personnel.
3. The investigator or authorized study personnel are responsible for study intervention accountability, reconciliation, and record maintenance (that is, receipt, reconciliation, and final disposition records).
4. Further guidance and information for the final disposition of unused study interventions are provided in the Pharmacy Manual.

